9.4 STATISTICAL ANALYSES

9.4.1 GENERAL APPROACH

Results will be reported using descriptive statistics (mean, 95%CI).

Normality of the distribution will be assessed (skewness and kurtosis). If not normally distributed, data will be transformed (Log_{10}) or non-parametric Kruskal-Wallis test will be used.

Bayesian repeated measures ANOVA will be used to analyze and compare baseline, 2 weeks, 4 weeks, 1 month and 6 months outcome measures.

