1 PROTOCOL SUMMARY

1.1 SYNOPSIS

Title:	Visual rehabilitation in a pediatric population of patients with homonymous hemianopia: a pilot study on virtual-reality stimulation.
Study Description:	Pilot, Open label, Non-randomized study to assess the feasibility of home-based audiovisual immersive virtual-reality stimulation in pediatric patients with homonymous hemianopia.
Objectives:	Primary Objective: Feasibility Secondary Objective: Visual acuity, reading speed, field of vision, quality of life.
Endpoints:	Primary Endpoint: Completion of the home-based audiovisual virtual-reality stimulation procedure (15 sessions).
Study Population:	Male and female patients > 8 years-old with diagnosed homonymous hemianopsia with no prior visual rehabilitation interventions. A total of 10 patients (5 with chiasmatic lesions and 5 with lesions outside of the optic chiasma)
Phase:	Pilot Study
Description of Study Intervention:	Home-based audiovisual immersive virtual-reality stimulation (15 minutes every 2 day for 4 weeks)
Study Duration:	2 years
Participant Duration:	7 months

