4 STUDY DESIGN

4.1 OVERALL DESIGN

We hypothesize that the home-based audiovisual 3D-MOT IVR stimulation program can be performed by HH pediatric patients and that this program will improve visual perception, reading speed and quality of life. For our trial design, we used the Pragmatic-Explanatory Continuum Indicator Summary (PRECIS-2) instrument, initiated and supported by the NIH Pragmatic Trials Collaborative Project to generalize knowledge about the conduct of pragmatic research. PRECIS-2 takes the innovative approach of translating ratings on nine domains related to trial design to a readily understood wheel format that communicates where the trial design falls on the explanatory (scored 1) - pragmatic (scored 5) continuum^{30,31} (Figure 1). All eligible patients in our study will be patients from care center at Sickkids, Toronto recruited through regular appointments made at the clinic (eligibility – recruitment). The setting of the trial corresponds to clinical visual care centers (setting). Information sheets will be given out to participants. Provider expertise corresponds to low-vision care center (organization). The group of patient will follow the study protocol from home, which can be usual practice in visual rehabilitation procedures. The delivery of the intervention is flexible with IVR stimulation every 2 days (± 1 day) at any time during the day (delivery). Adherence will be evaluated every 2 days; patients are free to “not-comply” and there will be no measures to improve adherence (adherence). Follow up of the primary outcome (adherence to the protocol) will be sent automatically through Wi-Fi to a dedicated and secured laboratory computer in real-time after each session. Secondary outcome will be assessed at the final visit after 4 weeks (follow-up secondary outcome at 1 month and 6 months). An Intention-to-treat will be performed for the analysis of the primary outcome (primary analysis). According to the PRECIS-2-wheel results (Figure 1), we propose an **interventional, pragmatic, single center pilot study** to assess **the feasibility and potential effectiveness of IVR stimulation in pediatric population of homonymous hemianopia patients**.

[figure not shown]

Figure 1: PRECIS-2 wheel indicating that our study is a pragmatic trial (scores >3).

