5.5 STRATEGIES FOR RECRUITMENT AND RETENTION

[name] and [name] will identify potential participants among their patients at the Hospital for Sick Children. Drs. [name] and [name] will make initial contact with potential participants. We will identify patients with homonymous hemianopia for a total of 10 participants. We will ensure 5 patients had lesions involving the optic chiasm and 5 not involving the optic chiasm

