9 STATISTICAL CONSIDERATIONS

9.1 STATISTICAL HYPOTHESES

- Primary Endpoint(s):

Feasibility is considered when the following primary endpoints criteria are met:

1. $\geq 8/10$ patient (80%) completed the protocol.
2. IVR stimulation protocol is considered complete if the patient performed ≥ 12 sessions out of 15.
3. ≤ 3 consecutive VRISE score < 25 per patient during the treatment period.
4. ≤ 2 dropouts (20%) for cybersickness (discomfort symptoms experienced in VR)

- Secondary Endpoint(s):

Secondary endpoint measures will be performed at Toronto Western hospital during baseline (visit 1), after 2 weeks (visit 2), after treatment at 4 weeks (visit 3) and at 1-month (visit 4) and 6 months (visit 5) follow-up. Results will be compared to baseline.

Visual acuity:

- Best Corrected Visual Acuity (BCVA) scores for distance and near vision – ETDRS/Colenbrander charts.
- Fixation stability - MAIA microperimeter, CentreVue
- Contrast sensitivity – FACT test.

Field of Vision:

- Humphrey full field 120 – Humphrey Field Analyzer 3, Zeiss
- Esterman binocular field - Humphrey Field Analyzer 3, Zeiss

Reading Speed:

- Minnesota Low Vision Reading - MNREAD test.

Quality of life:

- Children's Vision Function Questionnaire (39 questions)

- Exploratory Endpoint(s):

None

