9.4.2 ANALYSIS OF THE PRIMARY ENDPOINT(S)

We will visualize and report results using descriptive statistics (including frequency distributions, a measure of central tendency and a measure of dispersion) of secondary outcomes. Statistical comparison between the 2 conditions (baseline and after treatment) for the secondary outcomes will be made using two-way ANOVA with repeated measures. Statistical analyses will be performed by our colleague biostatistician and epidemiologist [name].

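### The only rank test named in section 9.4.1 is Kruskal-Wallis, an independent-groups test, while every comparison stated in section 9 is within child

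*Combined protocol and SAP*

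**What the plan says.** Section 9.4.1 (General approach) has normality assessed by skewness and kurtosis. Data that fail are to be log10-transformed, or "non-parametric Kruskal-Wallis test will be used". It gives no rule for choosing between the two routes and does not say which factor the rank test applies to.

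The comparisons stated in section 9 are:

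- Section 9.1, on the secondary endpoints at visits 1 to 5: "Results will be compared to baseline".
- Section 9.4.1: "Bayesian repeated measures ANOVA will be used to analyze and compare baseline, 2 weeks, 4 weeks, 1 month and 6 months outcome measures".
- The secondary-outcome text of section 9.4, which appears under heading 9.4.2: "Statistical comparison between the 2 conditions (baseline and after treatment) for the secondary outcomes will be made using two-way ANOVA with repeated measures". (Headings 9.4.2 and 9.4.3 look transposed. That may come from the reading of the PDF, and nothing here depends on it.)

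There is one treated group of 10 children. The only between-child split is lesion site. The synopsis gives it as "5 with chiasmatic lesions and 5 with lesions outside of the optic chiasma", and section 5.5 repeats it as a recruitment target: "We will ensure 5 patients had lesions involving the optic chiasm and 5 not involving the optic chiasm". Section 9 does not mention lesion site.

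**The concern.** Kruskal-Wallis ranks all values together and treats the sets being compared as different people. Here the sets are visits of the same children. With 10 participants and no control arm, each child's own baseline is the main source of precision, and a test that ignores it can miss a change that nearly every child shows. The outcomes concerned (acuity, fixation, contrast, fields, reading speed, quality of life) are those that section 4.1 uses to judge potential effectiveness.

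The intended use is also unclear. If the test is meant for visits, it is the wrong kind of test. If it is meant for lesion site, it is a valid kind of test, but the visit comparisons then have no rank test. The two model descriptions in 9.4 differ as well: one is Bayesian over five time points, the other a two-way repeated-measures ANOVA of two conditions whose second factor is not named.

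**Working it through.** **Figure to reproduce.** None. Section 9 states no significance level, effect size, SD or within-child correlation, and section 9.2 gives no calculation for the 10 patients.

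**Why pairing matters.** Let each visit have SD σ and let two visits of one child correlate at ρ. The within-child difference has variance 2σ²(1 − ρ), whereas an independent-groups test works as if it were 2σ². With σ = 1, the true variance against the presumed one is 2 v 2 at ρ = 0, 1.0 v 2 at ρ = 0.5, and 0.4 v 2 at ρ = 0.8. Kruskal-Wallis therefore becomes conservative as ρ rises and has nothing to lose at ρ = 0.

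**A worked case.** This is deliberately extreme. Take ten baseline values at the normal quantiles (i − 0.5)/10 and let every child improve by about 0.3 SD.

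- Kruskal-Wallis: the rank sums are 95 and 115. H = 12/(20 × 21) × (95² + 115²)/10 − 3 × 21 = 0.571, so p = 0.45.
- Exact signed-rank: all ten differences have the same sign, so p = 2/2¹⁰ = 0.002.

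**Simulation inputs.** From the documents: n = 10 and five visits. Assumed: two-sided 5%; ρ of 0, 0.3, 0.5 or 0.8; a shift of 0.8 SD, the same at every post-baseline visit; values formed as child effect plus visit error with total SD 1. Each setting has 4,000 trials, so the Monte Carlo standard error is at most √(0.5 × 0.5/4000) = 0.8 points. Kruskal-Wallis and Friedman use the chi-square reference; signed-rank is exact. Power is shown for skewed (exponential) data, because the fallback applies only to data judged non-normal.

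| Power, Kruskal-Wallis v paired test | ρ = 0 | 0.3 | 0.5 | 0.8 |
|---|---|---|---|---|
| Baseline v one later visit (signed-rank) | 61 v 45% | 53 v 55% | 52 v 66% | 58 v 91% |
| Same, 3 of 10 lacking the later value | 48 v 34% | 39 v 40% | 38 v 51% | 41 v 79% |
| Five visits (Friedman) | 53 v 46% | 38 v 56% | 36 v 68% | 33 v 91% |
| Same, 3 of 10 lacking both follow-up visits | 51 v 30% | 36 v 37% | 35 v 48% | 33 v 74% |

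In the rows with missing values, the paired tests use 7 children and Kruskal-Wallis uses all observed values.

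**False positives with no effect** (normal data, same four values of ρ):

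- Two visits: Kruskal-Wallis 5.5 / 2.5 / 1.1 / 0.1%; signed-rank 5.0 / 5.1 / 4.5 / 4.0%.
- Five visits: Kruskal-Wallis 5.0 / 1.2 / 0.3 / 0.1%; Friedman 5.0 / 4.8 / 4.5 / 4.7%.

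The 5.5% at ρ = 0 is consistent with the exact size of the chi-square version at 10 v 10, which is 5.24%. The test is therefore near or below nominal, not strictly below it.

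**The case against.** **The rank test may never be used.** Section 9.4.1 offers the log transformation as an alternative, and that route keeps the repeated-measures analysis. This stands. A reader might infer that non-normal data have no valid route at all; the text does not support that. What is missing is a paired *rank* route.

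**Kruskal-Wallis may be meant for lesion site.** A two-way ANOVA implies a second factor, and 5 v 5 by lesion site is a candidate, for which an independent-groups test would be valid. This stands as a possibility. The comparison is not stated, though, the conditions named are baseline and after treatment, and such a test would not replace the visit comparisons.

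**The loss depends on the correlation.** This also stands. At ρ = 0 Kruskal-Wallis has more power, and at 0.3 the two-visit results are about equal. Simulated normal data would show larger gaps, but they lie outside the fallback's trigger and are not relied on.

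**The stakes are small.** The tests serve secondary outcomes of a 10-child pilot, with descriptive reporting also planned. A reader might infer that false positives are inflated or that the feasibility conclusion is at risk. Neither follows: the error is towards conservatism, and the feasibility criteria in 9.1 are counts against thresholds.

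**No single visit is fixed as the lead comparison.** Section 4.1 says "Secondary outcome will be assessed at the final visit after 4 weeks", which might suggest 4 weeks. But the same section also defines change at 2 and 4 weeks, 9.1 compares all visits with baseline, and 9.4 does not date its after-treatment condition. A 4-week lead test would be a new choice, not a correction.

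**Conclusion.** The mismatch is certain from the text: the one rank test named does not fit any comparison that section 9 states. How much it matters is conditional. It bites only if data are judged non-normal, the rank route is taken instead of the log transformation, and the test is applied across visits. Under the assumed 0.8 SD shift with skewed data and complete values, baseline v one later visit loses about 14 points of power at correlation 0.5 (66 − 52) and 33 at 0.8 (91 − 58). There is no clear loss at 0.3, and at 0 Kruskal-Wallis is ahead by 16 points (61 − 45). Since the documents supply none of the correlation, the effect size or the significance level, these figures show the range and are not forecasts. This is a modest correction to the secondary analysis and worth making before the data are seen.

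**What to change.** In section 9.4.1:

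- For visit comparisons, replace Kruskal-Wallis with Wilcoxon signed-rank for baseline against a given visit, and with Friedman across visits on children with complete rows, stating how many children that is.
- Keep Kruskal-Wallis only if a chiasmal v non-chiasmal comparison is wanted. In that case state the comparison and apply the test to change from baseline.

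In 9.4.1 and the secondary-outcome text of 9.4, name one repeated-measures model with visit as the within-child factor. The Bayesian model can stay. Name the second factor, or drop the two-way wording if there is none.

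The cost is a few sentences in section 9.4 and no new data. There are three downsides:

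- Friedman drops children with any missing visit. With 3 of 10 lacking follow-up, its advantage at correlation 0.3 disappears (36% v 37%).
- Signed-rank has less power than Kruskal-Wallis if the within-child correlation is near 0.
- Signed-rank also loses children who lack the later value. With 3 of 10 missing, it has 34% against 48% at correlation 0 and is about equal at 0.3. The final visit that section 7 gives withdrawn children is not tied to a set week, so it need not fill that gap.

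The differences in visit numbering and field-test timing between sections 1.3, 3, 4.1, 8.1 and 9.1 are a separate item.

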9.4.3 ANALYSIS OF THE SECONDARY ENDPOINT(S)

As recommended by CONSORT guidelines, analysis will be performed following an Intention-To-Treat (ITT) approach³².

Primary outcome corresponds to the feasibility of the study in terms of adherence, retention rates and recruitment. We specified, a priori, 4 feasibility objectives for our pilot study to be considered successful:

1. $\geq 8/10$ patient (80%) completed the protocol.
2. IVR stimulation protocol is considered complete if the patient performed ≥ 12 sessions out of 15.
3. ≤ 3 consecutive VRISE score < 25 per patient during the treatment period.
4. ≤ 2 dropouts (20%) for cybersickness (discomfort symptoms experienced in VR)

9.4.2 ANALYSIS OF THE PRIMARY ENDPOINT(S)

We will visualize and report results using descriptive statistics (including frequency distributions, a measure of central tendency and a measure of dispersion) of secondary outcomes. Statistical comparison between the 2 conditions (baseline and after treatment) for the secondary outcomes will be made using two-way ANOVA with repeated measures. Statistical analyses will be performed by our colleague biostatistician and epidemiologist [name].

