9.2 SAMPLE SIZE DETERMINATION

The CONSORT guidelines state that sample size calculations may not be required for feasibility studies, however it is important that the sample be representative of the target study population³³. For this pilot study, we will recruit 10 patients.

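### Secondary outcomes have two unreconciled repeated-measures ANOVA plans, a Kruskal-Wallis fallback unsuited to repeated visits, and no missing-data method

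*Combined protocol and SAP*

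**What the plan says.** The methods for the secondary outcomes are spread over section 9.4 of the combined protocol and SAP. (The texts under headings 9.4.2 and 9.4.3 appear to be exchanged. I cite the printed headings and do not count this as a fault.)

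- **Five time points, Bayesian (9.4.1):** "Bayesian repeated measures ANOVA will be used to analyze and compare baseline, 2 weeks, 4 weeks, 1 month and 6 months outcome measures". No prior, decision threshold or software is given.
- **Two conditions, two-way (under 9.4.2):** "Statistical comparison between the 2 conditions (baseline and after treatment) for the secondary outcomes will be made using two-way ANOVA with repeated measures". The second factor is not named, nor is the visit that represents the post-treatment condition.
- **Distribution check (9.4.1):** "Normality of the distribution will be assessed (skewness and kurtosis"), with no cut-off and no statement whether it applies to raw values, changes or residuals. On failure, "data will be transformed (Log_{10}) or non-parametric Kruskal-Wallis test will be used", with no rule for choosing between the two.
- **Sample (9.2):** "For this pilot study, we will recruit 10 patients". No alpha, power, effect size or SD is given.
- **Missing data:** no method is stated. Section 7 gives withdrawn children a final visit whose secondary outcomes are analysed. Section 7.2 keeps their data unless they ask otherwise, and replaces them to reach 10 evaluable patients.
- **Visual fields:** the schedule in section 1.3 marks Humphrey and Esterman at baseline and days 28, 58 and 200, not at day 14. Section 4.1 lists both among endpoints measured at 2 and 4 weeks, and section 8.1 lists them for every study visit.

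**The concern.** The two ANOVAs differ in inferential framework, number of visits and number of factors. They can give different answers for the same outcome, and nothing says which will be reported. A before-and-after comparison in a single arm has one evident factor, time. Lesion site (five children with and five without chiasmal involvement) might be the second, but the plan does not say so.

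The fallback is a separate fault. Kruskal-Wallis treats the visits as independent groups of different children. Here the same children are measured each time, so differences between children stay in the error term and can hide a real change.

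Section 4.1 makes potential effectiveness a study aim, so these results are likely to inform any later trial. An estimate that depends on which sentence the analyst followed is a weak basis for that.

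**Working it through.** The plan states no power or calculated sample size, so there is no figure of its own to reproduce. The checks below show consequences. **Assumed, not in the documents:** two-sided alpha 0.05; normal data with equal correlation between visits of 0.5, 0.7 or 0.9; a true change of 1 SD of the paired difference, the same at all four later visits; and 5–20% of post-baseline visits missing, independently.

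**1. Room for choice between the ANOVAs.** A frequentist five-visit F test stands in for the Bayesian model, since no prior or threshold is given. A baseline-to-4-week paired t test stands in for the two-condition comparison. In simulation with n = 10 and no true change, reporting whichever is significant gives 8.4–8.9% false positives per outcome instead of 5%. If any of the four later visits could serve as the post-treatment one, the chance that at least one paired test is significant is 15–17%. With a 1 SD change, the two tests disagree in 15–16% of trials.

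**2. The distribution check at n = 10.** Take a flag when |z| > 1.96 for skewness or kurtosis:

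- SE(skewness) = √[6·10·9 / (8·11·13)] = √(540/1144) = 0.69
- SE(kurtosis) = 2 × 0.687 × √[99 / (7·15)] = 1.33

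Simulated flag rates are 38% for exponential data, 26% for lognormal data with sigma 0.5, and 7% for truly normal data. With critical values set so that normal data are flagged 5% of the time, the first two fall to 27% and 18%. Either way the check usually misses skewed data. Applied at each of five visits, it flags at least one in 18–29% of wholly normal data sets. The result also depends on a cut-off that the plan does not give.

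**3. Kruskal-Wallis on five repeated visits.** The SD of a change is √[2(1 − ρ)] times the SD of a single visit, so a 1 SD paired effect is a shift of 1.00, 0.77 and 0.45 visit SDs at ρ = 0.5, 0.7 and 0.9. Simulated results at n = 10:

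| ρ | Kruskal-Wallis power | Friedman power |
|---|---|---|
| 0.5 | about 41% | 72–74% |
| 0.7 | about 14% | 72–74% |
| 0.9 | about 0.5% | 72–74% |

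Separate runs agree within about 2 percentage points. With no true change, Kruskal-Wallis rejects in 0–0.3% of trials instead of 5%. The test is too conservative, and more so the better the measurements repeat.

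**4. Missing visits, if incomplete children were dropped.** Expected complete children = 10(1 − q)^k, with k = 4 later visits for the five-visit analysis and k = 1 for baseline to 4 weeks.

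| q | Five visits | Baseline to 4 weeks |
|---|---|---|
| 5% | 8.2 | 9.5 |
| 10% | 10 × 0.9⁴ = 6.6 | 9.0 |
| 15% | 5.2 | 8.5 |
| 20% | 4.1 | 8.0 |

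For baseline to 4 weeks, noncentral-t power at 1 SD is 80% with n = 10 and 75% with n = 9.

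**5. Visual fields.** On the section 1.3 schedule no child has a day-14 field test. A five-visit analysis of Humphrey or Esterman that required all visits would therefore have 0 of 10 complete children.

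**The case against.** The strongest reply is that little hangs on these models. This is a 10-child, single-arm feasibility pilot, its success criteria are completion, VRISE scores and dropouts, and section 9.2 notes that "The CONSORT guidelines state that sample size calculations may not be required for feasibility studies". Descriptive results with 95% intervals are planned anyway, and both ANOVAs could be run if one were declared primary. That stands, and it limits the severity. It does not reconcile the two sentences or make Kruskal-Wallis suitable. Kruskal-Wallis would be defensible for comparing the two lesion groups, but section 9.4 plans no such comparison.

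A reader might infer four stronger points, which the documents do not support:

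- **That the distribution check chooses between the two ANOVAs.** In 9.4.1 it leads only to a transform or Kruskal-Wallis.
- **That both analyses require complete cases.** No section says so. Dropping incomplete children is usual for classical repeated-measures ANOVA, but a Bayesian model may keep them, depending on an implementation that is not stated.
- **That the plan breaks an ITT promise for these outcomes.** The statement under 9.4.3 that "analysis will be performed following an Intention-To-Treat (ITT) approach" is followed directly by the feasibility criteria, and section 4.1 says: "An Intention-to-treat will be performed for the analysis of the primary outcome (primary analysis").
- **That children will certainly be lost and paired power will fall from 80% to 60%.** The 60% belongs to n = 7, which is five-visit attrition applied to a two-visit test. At 10% missing, the two-visit test has n = 9 and 75% power. Sections 7 and 7.2 also keep withdrawn children's final-visit data. They do not cover every missed follow-up visit, so some risk remains.

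**Conclusion.** The point holds in limited form. The same secondary outcomes have two analyses with no order between them, one lacking a named second factor and post-treatment visit. The distribution rule cannot be applied reproducibly, and one of its two outcomes is a test that does not fit the design. The largest quantified effect is that test's loss of power: about 41% falling to 0.5% as correlation rises from 0.5 to 0.9, against 72–74% for Friedman. This rests on normal, equally correlated data and a 1 SD paired effect. The false-positive figures also rest on the stand-in tests, so they illustrate the analyst's freedom rather than predict an error rate.

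Missing visits are a gap in the plan, not a demonstrated loss. The day-14 visual-field schedule is a plain inconsistency between section 1.3 and sections 4.1 and 8.1. The change should be made, but the primary feasibility conclusion does not depend on it.

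**What to change.** Name one main analysis for each secondary outcome, and delete the other ANOVA and the distribution-based switch. One suitable choice is a mixed model with visit as a categorical effect and a child random intercept, using all enrolled children and all available visits. It can be frequentist with small-sample degrees of freedom, or the Bayesian model already planned, with its prior stated. Other single pre-specified methods would also resolve the conflict. This one handles incomplete visits, and field outcomes measured at four visits, without dropping children; the plan should state the missing-at-random assumption behind it.

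Report the 4-week change from baseline with a 95% interval as the main contrast, which fits the assessment at the end of the 4 weeks described in section 4.1. Use a Wilcoxon signed-rank test of that change as the sensitivity analysis in place of Kruskal-Wallis. If lesion site is meant to be a factor, say so. Reconcile the day-14 visual-field entries in section 1.3 with sections 4.1 and 8.1.

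The cost is SAP wording and slightly more analysis work. No extra children are needed.
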